9.7.4 Sequence of Analyses

There will be a baseline analysis, 3 interim analyses and a final analysis. Interim analyses are mainly descriptive and for monitoring purposes. Multiplicity corrections will not be considered.

- Baseline analysis: baseline characteristics of patients initiating cladribine tablets, baseline PRO data, baseline laboratory data, baseline data on previous MS DMD use, relapses during the previous 2 years (or since MS diagnosis, if diagnosis <24 months), baseline MRI data and past treatment adherence will be analyzed.
- First interim analysis: safety, adherence and PRO data will be analyzed for the subset of the first 30 patients enrolled into the study at the 6-month time point. This will be conducted primarily for evaluation of safety.
- Second interim analysis: safety, adherence and PRO data will be analyzed as soon as 6-month data are available for all patients.
- Third interim analysis: full data analyses will be performed on the 12-month data for all patients.
- Final analysis: full data analyses will be performed on the 24-month data for all patients at the end of the study. The final analysis will include the endpoint analyses illustrated in Section 9.7.3 as well as a comparison of characteristics of patients completing the study vs. those who drop out.

9.8 Quality Control

This study will be monitored in accordance with the International Council for Harmonization (ICH) Note for Guidance on Good Clinical Practice (ICH Topic E6, 1996). The site Monitor will perform visits to the study site at regular intervals. Representatives of the Sponsor's Quality Assurance unit or a designated organization, as well as Health Authorities, must be permitted to inspect all study-related documents and other materials at the site, including the investigator Site File, the completed Case Report Form (CRFs), and the patients' original medical records/files. The protocol, each step of the data capture procedure, and the handling of the data, including the final study report, will be subject to independent Quality Assurance activities. Audits may be conducted at any time during or after the study to ensure the validity and integrity of the study data.

9.9 Limitations of the Research Methods

As this study is being conducted as an observational study, data will be collected in the context of routine clinical care and standard of care rather than with a mandated clinical visit and assessment completion schedule. This may lead to inconsistent and variable data collection across patients and may result in missing data or information bias. In addition, variability in the treatments received may limit interpretation of the results. However, the objectives of this study are to assess real-world effectiveness, safety and treatment patterns of cladribine tablets and therefore an observational design is the appropriate method to achieve the study objectives.

The patients enrolled in this study may not be generalizable to all patients in the US receiving cladribine tablets for RMS. This will be addressed by including a heterogeneous group of study sites that are broadly representative of MS care centers in the US.

9.10 Other Aspects

9.10.1 Independent Ethics Committee or Institutional Review Board

Prior to commencement of the study at a given site, the protocol will be submitted together with its associated documents (e.g. ICF) to the responsible Independent Ethics Committee (IEC)/Institutional Review Board (IRB) for its favorable opinion/approval. The written favorable opinion/approval of the IEC/IRB will be filed by the investigator and a copy will be sent to the Sponsor.

The study must not start at a site before the Sponsor has obtained written confirmation of favorable opinion/approval from the concerned IEC/IRB. The IEC/IRB will be asked to provide documentation of the date of the meeting at which the favorable opinion/approval was given, and of the members and voting members present at the meeting. Written evidence of favorable opinion/approval that clearly identifies the study, the protocol version, and the Patient Information and Consent Form version reviewed should be provided. Where possible, copies of the meeting minutes should be obtained.

Amendments to the protocol will also be submitted to the concerned IEC/IRB before implementation in case of substantial changes.

9.10.2 Monitoring

A CRO Monitor will perform monitoring both remotely and via visits to the site at intervals. Monitoring visits will involve checking of CRFs against original patient records and identification of any questions or problems related to study conduct or data collection. Investigators must therefore ensure that the Monitor has access to relevant documents during monitoring visits, and that they and/or relevant site staff members are available to discuss any issues that may arise.

The study Monitor will send monitoring reports to the Sponsor.

9.10.3 Health Authorities

Not applicable.

9.10.4 Quality Assurance

In compliance with regulatory requirements, the Sponsor, a third party on behalf of the Sponsor, regulatory agencies, or IRB/IECs may conduct Quality Assurance audits/inspections at any time during or following a study. The investigator must agree to allow auditors/inspectors direct access to all study-related documents, including source documents, and must agree to allocate his or her time and the time of his or her study staff to the auditors/inspectors in order to discuss findings and issues.

The protocol, each step of the data capture procedure, and the handling of the data, as well as the study report, may be subject to independent Clinical Quality Assurance. Audits may be conducted at any time during or after the study to ensure the validity and integrity of the study data.

9.10.5 Archiving

The archive should be maintained for the period specified by local regulations, where applicable. All original patient files (medical records) must be stored at the site (hospital, research institute, or practice) for the longest possible time permitted by the applicable regulations. In the absence of applicable regulations, the archive should be maintained for at least 5 years after the final study report or the first publication of study results, whichever comes later. In any case, the investigator should ensure that no destruction of medical records is performed without the written approval of the Sponsor.

10 Protection of Human Patients

10.1 Patient Information and Informed Consent

An unconditional prerequisite for a patient's participation in the study is his/her written or e-signed informed consent. The patient's written informed consent to participate in the study must be given before any study-related activities are carried out.

Adequate information must therefore be given to the patient by the investigator before informed consent is obtained (a person designated by the investigator may give the information, if permitted by local regulations). A patient information sheet will be provided by the Sponsor for the purpose of obtaining informed consent. In addition to providing this written information to a potential patient, the investigator or his/her designee will inform the patient verbally of all pertinent aspects

of the study (the language used in doing so will be chosen so that the information can be fully and readily understood by laypersons). Depending on national regulations, a person other than the investigator may inform the patient and sign the ICF.

The ICF must be signed and personally dated by the patient and the investigator. The signed and dated declaration of informed consent will remain at the investigator's site and must be safely archived by the investigator. A copy of the signed and dated information and consent form should be provided to the patient prior to participation.

Whenever important new information becomes available that may be relevant to the patient's consent, the written patient information sheet and any other written information provided to patients will be revised by the Sponsor and be submitted again to the IEC/IRB for review and favorable opinion. The agreed, revised information will be forwarded to each patient in the study. The investigator will explain the changes to the previous version.

10.2 Patient Identification and Privacy

A unique patient number will be assigned to each patient at inclusion. This number will serve as the patient's identifier in the study as well as in the study database.

The investigator must ensure that the patients' anonymity is maintained. On the CRFs or other documents submitted to the Sponsor, patients should not be identified by their names, but by their assigned identification numbers. If patient names are included on copies of documents submitted to the Sponsor, the names (except for initials) must be obliterated and the assigned patient numbers added to the documents.

The investigator should keep a separate log of patients' identification numbers, names, addresses, telephone numbers and hospital numbers (if applicable). Documents not for submission to the Sponsor, such as signed ICFs, should be maintained in strict confidence by the investigator.

Only authorized persons will have access to identifiable personal details, if required for data verification. The patient's original medical data that are reviewed at the site during source data verification by the Monitor, audits, and Health Authority inspections will be kept strictly confidential. The investigator agrees to provide direct access to these documents to the Sponsor and to Health Authority representatives. The investigator is responsible for retrieving information from personal medical records.

Data protection and privacy regulations will be observed in capturing, forwarding, processing, and storing patient data. Patients will be informed accordingly and will be requested to give their consent on data handling procedures in accordance with national regulations.

11 Management and Reporting of Adverse Events

11.1 Adverse Events

An AE is any untoward medical occurrence in a patient or clinical study patient administered a pharmaceutical product and which does not necessarily have a causal relationship with this treatment. An AE can therefore be any unfavorable and unintended sign (including an abnormal laboratory finding), symptom, or disease temporally associated with the use of a medicinal product, whether or not considered related to the medicinal product.

Adverse Drug Reaction

An ADR is a response to a medicinal product which is noxious and unintended.

Response in this context means that a causal relationship between a medicinal product and an AE is at least a reasonable possibility.

ADRs may arise from use of the product within or outside the terms of the marketing authorization or from occupational exposure. Conditions of use outside the marketing authorization include off-label use, overdose, misuse, abuse and medication errors.

Reports of Special Situations: Pregnancy, Overdose, Off-label Use, Misuse, Medication Error, Occupational Exposure, Lack of Therapeutic Effectiveness and Others

- Use of a medicinal product during pregnancy or breastfeeding: reports where embryo, fetus or child may have been exposed to medicinal products (either through maternal exposure or transmission of a medicinal product via semen following paternal exposure)
- Reports of overdose, abuse, off-label use, misuse, medication error or occupational exposure
- Lack of therapeutic effectiveness
- Prescription error/dispensing error, e.g. due to confusion of invented names of the medicinal products
- Drug interaction
- Suspected transmission of an infectious agent via a medicinal product
- Product complaints, including falsified product or counterfeit

Reports of special situation with no associated ADR will not be submitted to the authorities as Individual Case Safety Reports. They will be collected and considered in the study report or any interim reports, as applicable.

Serious Adverse Events/Serious Adverse Reactions

An SAE/Serious Adverse Reaction is any AE/ADR as defined above, which also fulfills at least one of the seriousness criteria below:

- Results in death
- Is life-threatening¹
- Requires in-patient hospitalization or prolongation of existing hospitalization
- Results in persistent or significant disability/incapacity
- Is a congenital anomaly/birth defect
- Is otherwise considered as medically important²

¹ Life threatening in this context refers to a reaction in which the patient was at risk of death at the time of the reaction; it does not refer to a reaction that hypothetically might have caused death if more severe.

 2 Medical and scientific judgment should be exercised in deciding whether other situations should be considered as serious reactions, such as important medical events that might not be immediately life threatening or result in death or hospitalization but might jeopardize the patient or might require an intervention to prevent one of the other outcomes listed above. Such important medical events should be considered as serious.

Examples of such events are intensive treatment in an emergency room or at home for allergic bronchospasm, blood dyscrasias or convulsions that do not result in hospitalization or development of dependency or abuse. As a guidance, the important medical event terms list is intended to be used for assessment of suspected ADRs (see EMA/207865/2017).

Any suspected transmission via a medicinal product of an infectious agent is also considered a serious ADR.

Adverse Events of Special Interest

An adverse events of special interest (AESI) is an AE of scientific and medical concern specific to the Sponsor's product or program, for which ongoing monitoring and rapid communication by the investigator to the Sponsor can be appropriate. AESIs for monitoring should then be collected following the procedure for an SAE described in Section 11.4. The following events will be considered AESIs:

- Severe lymphopenia: defined as Grade 3 (<500 to 200 cells per microliter) or Grade 4 (<200 cells per microliter)
- Severe infection
- Tuberculosis
- Herpes zoster infection
- Progressive multifocal leukoencephalopathy
- Other opportunistic infection
- Malignancy

Events that Do Not Meet the Definition of a Serious Adverse Event

Elective hospitalizations (e.g. an overnight stay to facilitate therapy) are not considered as SAEs. However, all events leading to unplanned hospitalizations or unplanned prolongation of an elective hospitalization (e.g., undesirable effects of any administered treatment) must be documented and reported as SAEs.

Events Not to Be Considered an Adverse Event

Medical conditions present and documented at study start, that do not worsen in severity or frequency during the study are defined as baseline Medical Conditions and elective procedures and are NOT to be considered AEs.

In this protocol, symptoms and signs of relapse or worsening of MS will be captured in the context of the effectiveness assessment and recorded on the relapse module of the eCRF. Therefore, symptoms, relapses or worsening of MS will not be considered as AEs nor captured on the AE module of the eCRF unless suspected to be related to cladribine tablets (i.e., worsening is not consistent with the anticipated natural progression of the disease).

11.2 Severity of Adverse Events

Investigators should assess the severity/intensity of any AE as follows:

- Mild: The patient is aware of the event or symptom, but the event or symptom is easily tolerated.
- **Moderate:** The patient experiences sufficient discomfort to interfere with or reduce his or her usual level of activity.
- Severe: Significant impairment of functioning: the patient is unable to carry out usual activities.

11.3 Causality Assessment of Adverse Events

Investigators must assess the causal relationship between AEs and study drug (including any other non-medicinal product, radiation therapy, etc.) considering temporal relationship between the AE onset and study drug administration, safety profile of study drug (known ADRs), the patient's condition (medical history, underlying disease), concomitant medication, and study procedures.

Related: Suspected to be reasonably related to any study medication.

Not related: Not suspected to be reasonably related to any study medication. A reasonable alternative explanation must be provided.

11.4 Recording of Adverse Events

The recording period for AEs begins when the patient is initially included in the study (date of signature of first informed consent) and continues at least to the end of the mandatory safety follow-up period (i.e. up to 24 months in most patients or up to 30 months in patients with delayed start of Year 2 treatment).

All safety data, as specified above, occurring during the study, must be documented by the investigator within 24 hours of awareness and recorded in the CRF, including its description, seriousness, severity (grading), duration (onset and resolution dates), causal relationship, any other potential causal factors, actions taken with the study drug (e.g. dose reduction, withdrawal), required treatment and outcome of the AE.

Note - Event term 'Death', 'Disability' and 'Hospitalization'

Death, disability, and hospitalization are considered outcomes in the context of safety reporting and not usually considered ADRs/AEs. Therefore, the primary cause of death, disability or hospitalization should be recorded and reported as an SAE/ADR, and the outcome should be recorded in a separate data field. However, a term for the outcome will be selected if it is the only information reported or provides significant clinical information.

If death occurs, the primary cause of death or event leading to death should be recorded and reported as an SAE. "Fatal" will be recorded as the outcome of this respective event and not be as separate event. Only if no cause of death can be reported (for example, sudden death, unexplained death), the death per se might then be reported as an SAE.

Reports of Special Situations (see definition in Section 11) are also to be recorded in the CRF following the AE procedure, even if occurring without AE.

Pregnancy and Breastfeeding. Pregnancy or breastfeeding must be recorded in the CRF and additionally be reported to the Sponsor immediately (within 24 hours of awareness) by using separate data collection forms for pregnancy, independent if an AE was reported or not (this includes male patients whose partner becomes pregnant during the cladribine treatment period). The outcome of the pregnancy should be followed up and reported to the Sponsor until delivery. In the event of a pregnancy occurring during the cladribine treatment period, the female patient must be discontinued from cladribine tablets immediately.

Request for immediate discontinuation of study drug. In accordance with the USPI, patients should discontinue cladribine tablets if they become pregnant during the cladribine treatment period, become infected with HIV, develop an active chronic infection (hepatitis or tuberculosis) or develop moderate or severe renal impairment (creatinine clearance <60 milliliter per minute).

11.5 Safety Data Collection for Reporting

Safety Data Collection Forms:

The following safety data collection forms are used in this study:

- (S)AE Report Form
- Pregnancy Report Form
- Parent-Child/Fetus AE Report Form
- AESI Report Form

Events to be reported:

The following events are to be reported to the PPDSafety Check Desk (via phone: PPD, fax: PPD, or e-mail: PPDwithin 24 hours of awareness:

- All SAEs (related or unrelated) are to be reported independent of their relationship to the study drug by entering the event onto the eCRF or via the SAE paper report form in the event of eCRF outage
- AESIs should be reported if non-serious via the eCRF or via the AESI paper reporting form in the case of an eCRF outage and if serious following the procedure for an SAE, as described
- Pregnancy or lactation is to be reported by entering the event of pregnancy on to the relevant eCRF pages in conjunction with completing and sending the Pregnancy Report Form
- All events that occur in a Child/Fetus of a pregnant woman who was exposed to the study drug are to be reported via the eCRF or via the paper reporting form in the case of an eCRF outage
- Special situations (see definition in Section 11, including pregnancy, overdose, off-label use, misuse, medication error, occupational exposure, lack of therapeutic effectiveness) should be reported on the (S)AE Report Form by indicating whether serious or not

Non-serious ADRs are to be directly transmitted to Sponsor Global Patient Safety electronically (to the e-mail [contact]), as automatically generated reports from eCRF/EDC system (transmitted no later than within 24h of awareness).

Procedure for Safety Data Reporting (Completion and Forwarding)

For any new events that are serious, fatal or related to a special situation the investigator/healthcare provider must immediately (within 24 hours after becoming aware of the event) report the event via the eCRF or via the paper reporting form in the case of an eCRF outage. For all events that are non-serious an electronic data transfer (or paper form in case of eCRF outage) must be transmitted within 4 calendar days to Sponsor, including the PPD Lifecycle Safety, if applicable. The investigator must respond to any request by CRO for follow-up information, as noted above for initial report. CRO should forward the follow-up information within 24 hours to Global Patient Safety, as noted above for initial reports. The Sponsor has to meet strict regulatory timelines associated with expedited safety reporting obligations.

PPD Safety Check Desk:

- E-mail: PPD
- Fax: PPD

Global Patient Safety:

- E-mail: PPD
- Fax: PPD

The data entered on the safety data collection forms must be consistent with the information recorded in the CRF. If some data are missing, the form should be completed with the available data and a follow-up report will be sent as soon as possible. The minimum information to be included in the initial report is the following:

- Investigator name and contact details
- Patient identification (e.g., ID number, gender, age)
- Product (including lot/ batch number)
- Description of SAE/ADR/fatal case/special situation

The report should contain causality and seriousness information (for AEs) and must be signed off by the investigator.

When AE information is communicated via telephone, a written/EDC report must be sent immediately within 24 hours thereafter by fax or e-mail. In such cases the "clock start" for case reporting to Health Authorities is the date and time of the telephone communication.

Exposure During Pregnancy

All pregnancies with an estimated conception date in the period from the date of informed consent signature (where applicable) until the last post-treatment safety visit, or as defined in the protocol, must be recorded by convention in the AE page/section of the CRF. The same rule applies to pregnancies in female patients and to pregnancies in female patients of male patients. The investigator must notify the Sponsor in an expedited manner of any pregnancy using the Pregnancy Report Form, which must be transmitted according to the same process as described for SAE reporting. The Sponsor must be notified about any pregnancy independent whether the pregnancy is associated with an AE related to cladribine tablets or not.

Investigators must actively follow-up, document, and report to the Sponsor on the outcome of all these pregnancies and deliveries even if the patient is withdrawn from the study. If an abnormal outcome occurs, the respective safety data collection form (Pregnancy Report Form, Parent-Child/Fetus AE Report Form) is to be completed and sent to the Sponsor.

Procedure for Follow-up Information

The investigator must promptly respond to any request by CRO for follow-up information or questions from the Sponsor or delegate, as noted above for initial report. Such requests will be sent to the investigator via the CRO Safety Check Desk. SAEs/ADRs, special situations and AESIs occurring during the study must be monitored and followed up by the investigator until stabilization or until the outcome is known, unless the patient has a fatal outcome or is lost to follow-up.

The investigator will ensure any necessary additional therapeutic measures and follow-up procedures are recorded and reported via a follow-up report form. For all serious cases/ADRs/fatal cases, special situations and AESIs, missing information such as outcome, confounders, and causality are to be provided. Additionally, follow-up information of non-serious ADRs may be required by the Sponsor for medical assessment. Reasonable attempts to obtain follow-up information must be made and documented.

Reporting of any new information on a previously reported event (follow-up) will follow the procedures and timelines of the original report.

CRO should forward the follow-up information within 24 hours to Global Patient Safety, as noted above for initial reports. The Sponsor has to meet strict regulatory timelines associated with expedited safety reporting obligations.

Abnormal Laboratory Findings and Other Abnormal Investigational Findings

No scheduled laboratory assessments are required by protocol. Nevertheless, laboratory data of medical importance, as deemed necessary and requested by the investigator as part of the patient's standard medical care, will be, when available, recorded into the eCRF by the investigator.

Abnormal laboratory findings and other abnormal investigational findings (e.g. on an electrocardiogram trace) should not be reported as AEs unless they are associated with clinical signs and symptoms or are considered otherwise medically important by the investigator or general practitioner. If an abnormality fulfills these criteria, the identified medical condition (e.g. anemia, increased alanine transaminase [ALT]) must be reported as the AE rather than the abnormal value itself.

Vital Signs, Physical Examinations, and Other Assessments

Weight will be collected at baseline when available.

Physical examination data will be collected during the course of routine clinical care. Abnormal physical examination findings should not be reported as AEs unless they are considered medically important by the investigator. If an abnormality fulfills these criteria, the identified medical condition must be reported as the AE rather than the abnormal physical examination finding itself.

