7.4 Cladribine Tablets

Cladribine (2-chloro-2'-deoxyadenosine [2-CdA]) is a synthetic anti-neoplastic drug that belongs to the subgroup of agents called purine analogs. In 2019, cladribine tablets were indicated for the treatment of patients with RMS, including relapsing-remitting multiple sclerosis (RRMS) and active secondary progressive multiple sclerosis (aSPMS), by the US FDA.

Three clinical trials for cladribine tablets have been completed (CLARITY, ORACLE MS and ONWARD), and data from these trials (Leist 2014; Montalban 2016; Giovannoni 2010), as well as the extension phase of the CLARITY trial (Giovannoni 2013) and the interim long-term follow-up data from a prospective registry (the PREMIERE registry), have provided information on the efficacy and safety of cladribine tablets. In total, the follow-up consisted of >10,000 person-years of exposure for both cladribine tablets and placebo, with over 8 years of follow-up for some patients.

In the CLARITY trial, patients with active RMS were randomized to placebo or cladribine tablets (3.5 or 5.25 mg/kg body weight) for 2 years; each dose showed significant benefits in rate of relapse, disability progression, and MRI measures (Giovannoni 2010). Treatment with cladribine tablets in CLARITY produced efficacy improvements that were maintained in patients treated with placebo in the extension phase (Giovannoni 2013).

Approximately 20% to 25% of the patients treated with 3.5 mg/kg as monotherapy developed transient Grade \geq 3 lymphopenia. Grade 4 lymphopenia was observed in 0.7% of patients. Overall, nearly 90% of patients recovered by the end of the trials. The remaining patients recovered during long-term follow-up without developing severe or opportunistic infections.

Herpes zoster infection is considered as an important identified risk of treatment with cladribine tablets. The observed incidence rates in the monotherapy oral cohort for herpes zoster infection were 0.86 adjusted adverse events (AEs) per 100 person-years for cladribine tablets 3.5 mg/kg vs. 0.20 for placebo, and for severe herpes zoster infection 0.9 vs. 0.5, respectively. The incidence of herpes zoster infection was higher during periods of Grade 3 or 4 lymphopenia compared to the time when the patients were not experiencing Grade 3 or 4 lymphopenia.

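### Whether an asymptomatic Grade 3-4 lymphocyte count reaches the AESI form depends on investigator judgement, because two protocol reporting rules are not reconciled

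*Protocol*

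**What the plan says.** - **AESI definition.** Protocol 11.1 says an AESI "is an AE of scientific and medical concern specific to the Sponsor's product or program". Its list opens with "Severe lymphopenia: defined as Grade 3 (<500 to 200 cells per microliter) or Grade 4 (<200 cells per microliter"). The definition is a count threshold and sets no condition on symptoms or importance.
- **AESI handling.** Protocol 11.1: "AESIs for monitoring should then be collected following the procedure for an SAE described in Section 11.4". Protocol 11.5: "AESIs should be reported if non-serious via the eCRF or via the AESI paper reporting form".
- **Laboratory findings.** Under its paragraph on abnormal laboratory findings, Protocol 11.5 says these "should not be reported as AEs unless they are associated with clinical signs and symptoms". The same sentence then gives a second ground for reporting: "or are considered otherwise medically important by the investigator or general practitioner". No exception for AESIs is written there.
- **General AE definition.** Protocol 11.1 counts as an AE any "unfavorable and unintended sign (including an abnormal laboratory finding), symptom, or disease temporally associated with the use of a medicinal product".
- **Where the counts go.** Protocol 9.1.1 and Table 1 (footnote f) collect ALC as available from routine practice. SAP 15.3 gives the proportion of patients in each lymphopenia grade at each time point, and a listing that flags out-of-range values.
- **AESIs as an endpoint.** Collecting all AESIs is a secondary objective (Protocol 8.2). SAP 5 lists AESIs as an endpoint and points to SAP 15. In the public text, SAP 15 specifies no AESI summary.

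**The concern.** An AESI is defined as a kind of AE. If a finding is not to be reported as an AE, a site can reasonably conclude that it does not belong on the AESI form either. For an asymptomatic Grade 3 or 4 count, the AESI list and the laboratory paragraph can therefore point in opposite directions, and the outcome turns on whether a clinician regards the count as medically important.

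Two things are at stake. The number of severe-lymphopenia AESIs taken from the forms would mix true frequency with local reporting habit, and the error can only be downward. A count that appears only in a haematology table also lacks what an AESI record carries under Protocol 11.4 and 11.5: causality, action taken, outcome, and follow-up until stable. Protocol 7.4 notes that herpes zoster, itself an AESI, was more frequent during Grade 3 or 4 lymphopenia, so incomplete lymphopenia records would also make that event harder to interpret.

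**Working it through.** The plan states no figure to reproduce. The check is mainly a comparison of rules.

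**1. The rules side by side, for a count below 500 per microliter**

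| Symptoms | Judged medically important | AESI rules (11.1, 11.5) | Laboratory paragraph (11.5) | Agree? |
|---|---|---|---|---|
| Yes | Either | Report | Report | Yes |
| No | Yes | Report | Report | Yes |
| No | No | Report | Do not report | **No** |

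The conflict is confined to the last row. No section says which rule prevails there.

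**2. Is this a frequent AESI?** Protocol 7.4 gives "Approximately 20% to 25% of the patients treated with 3.5 mg/kg as monotherapy" for Grade 3 or higher lymphopenia. For other AESIs it gives rates under 3.5 mg/kg monotherapy. Assuming a constant rate, and that the opportunistic-infection figure uses the same unit, two-year risk = 1 - exp(-2 x rate):

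- herpes zoster, 0.86 per 100 person-years: 1 - exp(-0.0172) = 1.7%
- severe infection, 0.84: 1 - exp(-0.0168) = 1.7%
- opportunistic infection, 1.08: 1 - exp(-0.0216) = 2.1%

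On the protocol's own background data, severe lymphopenia is the commonest of these.

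**3. How much could be missed?** Let p be the frequency and f the share of cases that reach the form. Form-based AESI patients per 100 = 100 x p x f. The documents give no value for f, or for the share of cases without symptoms. The values of f below are assumptions.

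| f (assumed) | p = 20% | p = 25% |
|---|---|---|
| 100% | 20 | 25 |
| 50% | 10 | 12.5 |
| 25% | 5 | 6.25 |

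The table only restates the chosen f. It shows sensitivity to reporting and does not estimate a loss. Results are per 100 patients because the study-size section is not in the public text.

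**4. Do the ALC tables fill the gap?** The units match: 500 per microliter is 0.5 x 10^9/L, the upper limit of Grade 3 in SAP 15.3. The table is by time point, however. If proportions a and b are Grade 3-4 at two visits, the proportion ever Grade 3-4 across them lies between the larger of a and b (same patients) and a + b (different patients), and the table cannot say where. SAP 9 analyses endpoints without a window by eCRF visit, if available, and SAP 15.3 does not say where unscheduled counts go. The listing allows a patient-level check by hand, but no such derivation is planned.

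**5. Timing.** Protocol version 7.0 is dated 14 February 2024. Last patient last visit is planned for 30 March 2024 (15 + 30 = 45 days later) and database lock for 3 June 2024 (a further 1 + 30 + 31 + 3 = 65 days). SAP 4.0 still carries a placeholder date in 2024.

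**The case against.** The strongest reply is that the rules can be read together. The laboratory paragraph has its own exception for findings considered medically important, and a count that the protocol lists by name as being of medical concern fits it naturally. Other text points the same way: a dedicated AESI form, follow-up of AESIs until stable, and Protocol 9.1.1 singling out the same thresholds of 500 and 200. The general AE definition includes laboratory findings. The paragraph's closing instruction, to report the condition and not the value, is met by the term lymphopenia.

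Much of this stands. An investigator may report every such count, and many probably would. But the protocol does not say that AESI status settles medical importance; it leaves that to the investigator or general practitioner. Nor does it say that the specific rule overrides the general one. The closing instruction applies only once a finding has met the paragraph's criteria.

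It is also fair that SAP 15.3 shows Grade 3-4 frequency without relying on the AE form. That removes most of the risk of losing the signal. It does not supply a per-patient incidence or a check on the forms. Protocol 9.6 requires AESIs to be reconciled before lock but does not mention checking them against laboratory values.

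**Conclusion.** The point holds as an unreconciled wording conflict with a limited consequence. An asymptomatic Grade 3-4 count that the investigator does not consider important is an AESI under Protocol 11.1 and not reportable as an AE under the laboratory paragraph of 11.5. The form-based AESI count can therefore be biased downward, by an amount the documents do not allow anyone to calculate.

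A reader might infer that most severe lymphopenia will go unrecorded, or that the reported AESI rate could fall to half the true rate or near zero. The documents do not support that. Such figures need an assumed share of asymptomatic cases and an assumed share withheld, and neither is given. The 20% to 25% comes from completed trials and is not a forecast for this cohort. The counts also still reach the haematology tables and listings, so the risk is that an event is missing from the AE or AESI form, not from the study.

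The remaining gaps are the absence of a worst-grade-per-patient summary and, in the public text, of any AESI summary in SAP 15.

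**What to change.** **Protocol.** Reconcile the AESI list in 11.1, the AESI reporting rule in 11.5 and the laboratory paragraph in 11.5 with one sentence stating whether a count that meets the AESI definition is reported regardless of the laboratory paragraph. So close to last patient last visit this will do little for prospective reporting, but it settles how counts already collected are to be queried.

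**SAP.** In section 15:

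- derive each patient's worst post-baseline ALC grade from all recorded counts, scheduled or not, and show how many patients have no post-baseline count;
- report the proportion with any ALC below 0.5 x 10^9/L beside the number with a severe-lymphopenia AESI on the form;
- list patients for whom the two sources disagree, and resolve these before database lock as part of the AESI reconciliation that Protocol 9.6 already requires.

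**Cost.** One protocol sentence, a small amount of programming on data already in the eCRF, and some additional AESI queries to sites. Because ALC is collected only as available, the laboratory-based proportion remains a minimum.
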